8.1 Adjudication Procedure

Each AE will be reviewed individually by a DMC/CEC. The DMC Charter is provided as **Appendix V**. Each event is initially classified as an adverse event or a non-event. A non-event is an event that does not require treatment. An event captured and determined to be a non-event will be reported as an observation. Following this determination, an adverse event is assessed for relatedness to the trial and may be classified as a study-related adverse event or a not-study-related adverse event. A not-study-related adverse event is an adverse event determined to not have a causal relationship with either the device or the procedure. All study-related adverse events are further adjudicated for severity and relatedness to the procedure/device as defined below.

Event severity refers to the degree of seriousness of the AE. The categories of event severity are: Serious Adverse Event (SAE) and a rating of mild, moderate or severe. Event relatedness refers to the association to the investigational device, fixation hardware or the surgical procedure. Event relatedness is categorized by the following associations: device related, hardware related, procedure related, other related, or unknown (undeterminable) relatedness.

For clarification, the following “relatedness” definitions will be applied in this investigation:

- **Device Related:** An adverse event that results from the presence or performance of the SIFS mesh device.
- **Hardware Related:** An adverse event that results from the presence or performance of any of the supplemental fixation device components.
- **Procedure Related:** A procedure related adverse event shall be evaluated and adjudicated in accordance with the below sub-classifications. A procedure related AE may occur as a result of one or more of the following and shall be specified as such for analysis and reporting purposes:
 - *Procedure – Device:* Occurs due to the implantation procedure for the investigational mesh device
 - *Procedure – Hardware:* Occurs due to the implantation procedure for the supplemental fixation
 - *Procedure – General Surgery:* Occurs as a result of the general surgical procedure and is not related to any of the above defined definitions or any of the below definitions.
- **Other Related:** An adverse event that occurs and is determined to have a relatedness that is not device, hardware, procedure, general surgery, or unknown relatedness.
- **Unknown:** An adverse event that cannot be determined to have a causal relationship with either the device or procedure will be classified as unknown.

It is anticipated that resultant of the defined criteria for each relatedness determination, few adverse events will be categorized as “Other”. The severity of events will be classified by the DMC as described in the following two sections.

8.2 **Serious Adverse Event**

The DMC will first determine whether an AE is serious. A Serious Adverse Event, corresponding to FDA’s definition, is an adverse event that results in one of the following outcomes:

- requires hospitalization,
- prolongs hospitalization,
- is life-threatening,
- results in a congenital anomaly/birth defect, or
- results in death.

8.3 **Event Severity**

The DMC will adjudicate the severity of each AE. Severity is categorized as follows:

- **Severe Adverse Event:** Significant impairment of functioning; subject is unable to carry out usual activities. A severe AE requires treatment or intervention.
- **Moderate Adverse Event:** Subject experiences sufficient discomfort to interfere with or reduce their usual level of activity. A moderate AE requires treatment.

- **Mild Adverse Event:** Subject is aware of event or symptom, but event/symptom is easily tolerated. A mild AE may not require treatment.

The Clinical Event Committee shall be convened on a quarterly basis through the duration of the investigation to formally review and adjudicate study events. The DMC Chairperson shall perform an interim (continuous) review of adverse events prior to conducting the quarterly committee review(s). The Chairperson may convene a Committee meeting at his/her discretion at any time to ensure subject safety is adequately protected.

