8.0 SAFETY EVALUATION

Safety of the Spineology Interbody Fusion System will be determined through the reporting process for Adverse Events. All adverse events, whether felt to be device-related or not, are to be reported and followed at each study interval to resolution, or for events that remain unresolved, until the subject concludes study participation. Information captured will include the type and description of the event, date of onset, treatment required and resolution status. The investigator shall additionally provide any supplemental information pertinent to the overall evaluation of the event. All reported events will be reviewed and adjudicated by an independent Data Monitoring Committee (DMC)/Clinical Events Committee (CEC).

For this investigation, an adverse event is defined as a secondary disease or condition that develops in addition to, or at an increased rate or severity from, the expected response to treatment, necessitating further evaluation and treatment by a physician. An adverse event may be an undesirable clinical occurrence, subject complaint, change in health status, or product issue. A clinical event will not be reported if it existed at the time of enrollment and continued unchanged thereafter, unless the event worsened considerably requiring additional medical or pharmacological treatment. Adverse Event reporting begins during the study treatment surgical procedure.

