Functional Disability – In this investigation, functional disability is defined as the subject's self-rated score on the Oswestry Disability Index. The ODI is a commonly used 10 question instrument for assessing patients with back pain. The greater the score achieved, the greater the functional disability. A lower ODI score indicates less back disability (greater back function). A 15 point difference compared to baseline is considered clinically significant.

Hardware Related AE – An adverse event that results from the presence, performance or implantation of the supplemental fixation device hardware or its components.

Informed Consent – A process by which a subject voluntarily confirms his or her willingness to participate in a particular investigation, after having been informed of all aspects of the investigation that are relevant to the subject's decision to participate. Informed consent is

documented by means of a written, signed, and dated informed consent form approved by the site's reviewing IRB.

Institutional Review Board (IRB) – An independent body (a review board or a committee, institutional, regional, or national (centralized) constituted of medical/scientific professionals and non-medical/non-scientific members, whose responsibility it is to ensure the protection of the rights, safety, and well-being of human subjects involved in an investigation and to provide public assurance of that protection, by among other things, reviewing and approving/providing favorable opinion on the investigation protocol, the suitability of the investigator(s), facilities, and the methods and materials to be used in obtaining and documenting informed consent of the investigation subjects.

Low Back Pain (LBP) – For this investigation, LBP is defined as the self-rated score a subject indicates on a Visual Analog Scale during normal daily activities. When interpreting the VAS, a higher score indicates a greater level of pain severity and a lower score indicates a lesser severity of pain. LBP is captured on a 100mm VAS. A 20mm difference when compared to baseline is considered clinically significant. The same measurement system/guideline is employed for leg pain.

Not Study-Related AE – An event adjudicated by the DMC CEC and determined to not have a causal relationship with either the device or the procedure.

Observation – An observation is an event adjudicated by the DMC CEC and determined to be a non-event and did not require treatment.

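### Section 8.1 makes treatment the only test for an adverse event, which conflicts with the mild-AE definition in 8.3 and leaves untreated events out of the AE tables

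*Combined protocol and SAP*

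**What the plan says.** Section 8.1 sets the order of adjudication: "Each event is initially classified as an adverse event or a non-event". The test follows at once: "A non-event is an event that does not require treatment". Such an event is kept under another label: "An event captured and determined to be a non-event will be reported as an observation". The Observation entry in section 11.0 repeats the rule ("determined to be a non-event and did not require treatment"). The AE definition in 8.0, repeated in 11.0, also contains a treatment condition: "necessitating further evaluation and treatment by a physician". A later sentence in 8.0 lists what an AE may be, without mentioning treatment: "An adverse event may be an undesirable clinical occurrence, subject complaint, change in health status, or product issue".

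Section 8.3 grades severity. For the lowest grade it says "A mild AE may not require treatment"; for the next, "A moderate AE requires treatment"; the severe grade likewise requires treatment or intervention.

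Section 8.2 defines a serious adverse event by outcome (hospitalization, prolonged hospitalization, threat to life, congenital anomaly, death), but as a kind of adverse event. The Study-Related Event entry in 11.0 sends all events to FDA but admits only study-related AEs to the final statistical analysis. The safety component of the primary endpoint in 3.2.1 and 3.2.6 fails on an investigational-device-related SAE at the index level; section 2.2 adds secondary surgical interventions at that level.

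**The concern.** The rule that decides whether something is an AE disagrees with the rule that grades AEs. Two adjudicators, one following 8.1 and the other 8.3, would classify the same untreated, easily tolerated event differently, and the choice decides whether it is counted. Section 8.0 says that device safety is determined through AE reporting, so this classification largely defines the safety result. With no control arm, no comparison group shares the under-count, and the bias favours the device.

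The order of the steps raises a second, smaller issue. The treatment test comes before the seriousness question and has no exception for an event with an 8.2 outcome. The primary safety component could therefore miss such an event.

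**Working it through.** **1. Trace events through the text as written.** The events are illustrations; the documents give no counts.

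| Event | Under 8.1 | Under 8.0, 8.2 or 8.3 | Where it is reported |
|---|---|---|---|
| Easily tolerated symptom, treated | AE | Mild AE | AE tables, if study-related |
| Easily tolerated symptom, untreated | Observation | Mild AE | No AE table |
| Mesh tear, left alone | Observation | Listed device risk (7.2.1); product issue (8.0) | No AE table; 3.2.7 tabulates device position, not condition |
| New neurological deficit, watched only | Observation | Grade depends on effect on activity | Neurological status summary, without relatedness |
| Device-related event, stay prolonged for observation only | Observation, if such a stay is not treatment | Has an 8.2 outcome | No AE table; cannot fail the safety component |

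**2. Is 8.3 only loose wording?** The severe and moderate grades say that treatment is required, and only the mild grade says that it may not be. The distinction looks deliberate. Under 8.1 it can never apply, because an untreated event does not reach grading.

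**3. Effect on the tables.** Section 3.2.7 plans the proportion of subjects with any study-related AE, a subject-level table by event type, and event-level tables by severity and relatedness. Under 11.0 observations enter none of them. The AE numerators can only fall and the denominator (all treated subjects) is unchanged, so the bias is downward. Its size cannot be computed from the documents.

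**4. Reproduce the plan's sample size.** Inputs from 3.2.4: null 0.55, alternative 0.68, one-sided alpha 0.05, exact binomial test. At n = 87 the smallest r with P(X ≥ r | 0.55) ≤ 0.05 is r = 56. The attained alpha is 0.0487 and the power at 0.68 is 0.801; 87 is the first n to reach 80%. Then 87/0.85 = 102.4, against the stated 102. The plan's figure reproduces.

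**5. Sensitivity of the primary test.** Assume all 102 subjects have an outcome. P(X ≥ 65 | 0.55) = 0.0464 and P(X ≥ 64 | 0.55) = 0.0697, so 65 successes are needed. One subject is 1/102 = 1.0 percentage point. This shows that one subject matters at the boundary; it does not measure the flaw.

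**6. Illustration under an assumption.** Suppose the true success rate is 0.55 and a net 1, 2 or 3 percentage points of subjects count as composite successes only because an untreated device-related serious event was called a non-event. The chance of passing is P(X ≥ r) at 0.56, 0.57 and 0.58:

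| n (r) | No misclassification | 1 point | 2 points | 3 points |
|---|---|---|---|---|
| 87 (56) | 0.049 | 0.071 | 0.100 | 0.137 |
| 102 (65) | 0.046 | 0.070 | 0.101 | 0.142 |

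The 1 to 3 points are assumed, and nothing in the documents supports a particular value. They are net of the other components: a subject who fails pain, function or fusion is a failure whatever happens to the safety call.

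**The case against.** The strongest reply is that the conflict is one sentence in 8.3 against a treatment test used consistently in 8.0, 8.1 and 11.0, and that nothing is hidden. Non-events are reported as observations, 9.4 has the committee review all events for unanticipated device effects, and every event goes to FDA. Neurological status and device position have their own summaries, and the core lab reads device condition and migration (6.0). The word treatment is not defined, so a committee could regard an inpatient stay as treatment. The DMC Charter (Appendix V) is not in the text available here and may settle the order of review.

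Much of this stands, and it rules out several stronger readings that a reader might infer:

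- That untreated events are discarded. They are kept and reported, but outside the AE analysis.
- That the mild category is empty. Treated mild events remain in it.
- That 8.1 contradicts the SAE definition. Section 8.2 defines an SAE as a kind of AE, so what exists is an ordering gap.
- That each missed serious event adds a success. It does so only if the subject also meets pain, function and fusion.
- That an untreated tear, migration or deficit affects the primary endpoint. Without an 8.2 outcome it could not fail the safety component in any case.

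The secondary-surgery criterion in 2.2 opens no further route, since an event that leads to surgery has been treated.

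The reply does not remove the conflict between 8.1 and 8.3 or the exclusion in 11.0. The separate summaries carry no relatedness or seriousness call, and 3.2.7 specifies no table for device condition, so an untreated mesh tear appears in no specified table. A clarifying charter would still leave the protocol's own sections in disagreement.

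**Conclusion.** The point holds in two parts of unequal weight. The first is firm: 8.1, with 8.0 and 11.0, conflicts with 8.3 on untreated events, and following 8.1 biases the AE, severity and relatedness tables downward. The direction follows from the text; the size is unknown. The second is conditional: on a literal reading of 8.1 and 8.2, an untreated device-related event with a serious outcome is never assessed for seriousness, and the subject can pass the safety component. This needs a rare combination, a narrow reading of treatment, and success on the other three components. The pass probabilities of 0.070 to 0.142 at n = 102 are conditional on an assumed 1 to 3 points of misclassification and are not estimates for this trial. The documents do not support a claim that serious events will in practice be lost from the primary endpoint.

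**What to change.** Reconcile 8.0, 8.1, 8.3 and the Adverse Event and Observation entries in 11.0 as follows, and bring the DMC Charter into line.

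1. Remove treatment from the AE/non-event decision in 8.1, from the Observation entry and from the AE definition in 8.0 and 11.0. The definition must change too, because a site that applies it may never report an untreated event to the committee. The clause in 8.0 on pre-existing conditions also turns on added treatment and should be checked with it.
2. Apply the 8.2 criteria and the device-relatedness assessment to every captured event before any non-event decision, and state that an event with an 8.2 outcome cannot be an observation.
3. In 8.3, grade by effect on the subject. If the moderate and severe grades still require treatment, an untreated event that limits activity has no grade.
4. Tabulate observations by type and relatedness beside the AE tables in 3.2.7, and amend the Study-Related Event entry in 11.0 to allow this.

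The change is mainly wording. The committee already reviews every reported event, so the added adjudication and tabulation work is small. Reported AE rates will be somewhat higher. The change should be in place before adjudication starts, because later reclassification would be made with outcomes known.

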9.0 ETHICS

This investigation will be conducted in accordance with ethical principles having their origins in the Declaration of Helsinki. This investigation will further be conducted in accordance with applicable federal regulations, specifically, the Title 21 Code of Federal Regulations, Part 812 – IDE Regulations, Part 50 – Informed Consent, Part 54 – Financial Disclosure, Part 56 – IRBs, ISO 14155 (2012), and ICH E6 – Good Clinical Practices (GCPs) Consolidated Guidance.

9.1 INSTITUTIONAL REVIEW BOARD (IRB)

Prior to participating in this investigation, the clinical site will be responsible for obtaining approval from their governing IRB. The Principal Investigator (PI) at the site is responsible for obtaining and maintaining IRB approval to participate in this investigation. A copy of the initial and all periodic review and approvals shall be maintained in the investigative site's administrative binder. A copy of each approval shall be provided to Spineology as the study sponsor and shall be maintained in the respective site administrative files.

9.2 INFORMED CONSENT

Prior to enrolling subjects into this investigation, a site-specific IRB approved Informed Consent Form (ICF) is required. The PI at each site is responsible for obtaining and maintaining the site-specific approved ICF. A copy of the site-specific initial ICF, and any subsequent approved revisions of the ICF, will be provided to Spineology in a timely manner for maintenance in the respective site-specific administrative file.

Subject participation in this investigation is voluntary. In accordance with FDA regulation 21 CFR, Part 50, written informed consent is required of all subjects (or their legal representative) prior to study participation. ***Spineology is required to report any failure to obtain subject consent to FDA within 5 working days of learning of such an event (21 CFR, §812.150(b)(8)).***

A sample Informed Consent Form Template for this investigation is provided as **Appendix VI**.

9.3 PATIENT DATA CONFIDENTIALITY

All information and data provided to Spineology concerning subjects and their participation in this clinical investigation will be considered confidential by Spineology. Only authorized sponsor personnel or an appropriately identified FDA representative will have access to these confidential files. All data used in the analysis and reporting of this investigation will be without identifiable reference to specific subject names. Subjects will be identified by a three (3) digit (sequential)

number and a three (3) letter name code. The name code will be determined using the subject's first-middle-last initials. As an example, a subject named John Quincy Smith would have a name code of JQS. In the event a subject does not have a middle name, a dash (-) shall be used in its place. Further, each investigative site is assigned a three (3) digit number as the site identifier code by the sponsor. The site ID together with the subject ID and name code shall constitute the complete subject ID. As an example, if John Quincy Smith was the first subject enrolled at a site assigned a site ID code of 123, he would be identified as subject 123-001 JQS. All subject IDs are unique to the site/subject.

Data collected in this investigation will be obtained in compliance with applicable federal regulations relating to confidentiality and security of protected health information (PHI) including by not limited to the Health Insurance Portability and Accountability Act (HIPAA). HIPAA regulations require a signed subject authorization, which informs the subject of the following:

- What PHI will be collected from trial subjects,
- Who will have access to that information and why, and
- Who will use or disclose that information.

In the event that a subject revokes authorization to collect or use PHI, the Investigator, by regulation, retains the ability to use all information collected prior to the revocation of subject authorization. For subjects who have revoked authorization to collect or use PHI, attempts should be made to obtain permission to collect at least vital status (i.e., that the subject is alive) at the end of their scheduled trial period.

In accordance with HIPAA regulations, subject records leaving the facility for purposes of the investigation should be identified by the Subject ID assigned for the trial and should not include the subject's name, whenever practical. Every effort should be made to "black out" (redact) the subject's name from medical records, including x-rays, prior to sending to Spineology.

This trial is being conducted in compliance with FDA 21 CFR and all personal information pertaining to subjects will be kept confidential. Whenever practical, subjects will be identified only by their subject ID number and initials. Clinical trial documents and hospital and clinic medical records pertaining to trial subjects may be reviewed by Spineology trial personnel or their representatives, FDA, or other health inspectors as needed to assure compliance with trial requirements.

Information obtained in the course of executing this trial, including still and motion photography, may be presented for regulatory, clinical or educational purposes provided no subject is identified. The information collected is the property of Spineology.

9.4 DATA MONITORING COMMITTEE (DMC)

An independent Data Monitoring Committee will be established for this investigation and will function as an advisory group to provide independent oversight of the investigation and to ensure patient safety. The DMC shall be comprised of no less than three (3) physician consultants of appropriate training, expertise and experience in the spinal discipline and a biostatistician. A DMC Chairperson shall be designated to preside over DMC meetings. The DMC may function in the role of a Data Safety Monitoring Board (DSMB) and as a Clinical Events Committee (CEC). The complete DMC Charter is provided as **Appendix V**.

DMC DSMB primary responsibility is to ensure subject safety. Additional DMC DSMB responsibilities may include, but are not limited to, review of interim analyses of outcomes, safety data summaries and study performance information. In addition, the DMC DSMB may provide recommendations relative to the study design, stopping rules for trial conduct, and determinations for continuance, modification, or termination of investigation conduct. DMC DSMB meetings will be conducted no less than annually.

DMC CEC responsibilities include review and adjudication of all adverse events reported for this investigation. The DMC CEC shall adjudicate events for seriousness, relatedness and severity. The DMC CEC shall review all events for potential UADE occurrence. DMC CEC meetings shall be conducted on a quarterly basis throughout the duration of this investigation.

